Release of any information from the patient's journal to the person in charge of the study will take place according to section 46, subsection 1 of the Danish Health Act. According to this section, information about an individual person's health, other private conditions and confidential information in patient journals etc. may be released to a researcher for the use in a concrete biomedical research project. Information about gender distribution, population distribution within various age groups, age distribution, blood pressure and weight may be obtained from a patient's journal. In addition, information may be obtained about symptoms in relation to PAH, medical treatment and possible concomitant diseases. This kind of information may be compared with data appearing from the loop recorder and the MR scans. Any information used for publication will be anonymized.

We adhere to the European regulation on protection of personal data.

The study has been announced to and approved by the Danish Data Protection Agency (J.nr. 2018-41-5331<)

ASPIRE: ArrhythmiaS in Pulmonary arterial hypertension and right heart failure assessed by continuous long-term cardiac monitoring

Financial conditions:

We will apply for funding from external foundations. We will keep The Danish Scientific Ethical Committee currently informed about funding and also notify them when the final funding has taken place.

The study has been started by the initiative of consultant [name]

Recruitment of patients

The patients will be recruited from the cohort already treated at "Kardiologisk Klinik" for PAH. In addition, we will prospectively offer new patients participation in the study and obtain their acceptance.

Publication of test results:

We aim at publishing all results, whether positive, inconclusive or negative, in articles in international scientific journals. Such articles will be found on the internet at www.ncbi.nlm.nih.gov/pubmed by a search on "[name]" and "[name]" and the subject "pulmonary arterial hypertension". If the test results are not accepted by international journals publication of the results will be made in national journals and in presentations at national and international conferences.

Abbreviations

2-DE	2-dimensional echocardiography
6 MWT	6-Minute Walk Test
AF	Atrial Fibrillation
AFL	Atrial Flutter
AVNRT	AtrioVentricular Nodal Reentry Tachycardia
BNP	Brain Natriuretic Peptide
CMR	Cardiac Magnetic resonance imaging

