Figure 3 The Medtronic CareLink Network is fast and easy to use with scheduling flexibility, allowing patients to transmit data within a time range rather than at a set time. Clinic staff need not be present during transmissions.

Study Synopsis – ASPIRE I

Name of the study	Incidence and characteristics of supraventricular and ventricular arrhythmias in PAH (ASPIRE-I)
Study design	Single centre observational study in patients treated with PAH specific medication. Patients will be followed for 2 years after inclusion.
Study objectives	Primary objective To assess the incidence of arrhythmias in prevalent and incident cases of PAH using continuous long-term monitoring by Reveal LINQ insertable cardiac monitor. To assess heart rate variability in correlation to known risk markers in PH.
Methodology	The study will be conducted as a single center study at Copenhagen University Hospital, Rigshospitalet, DK-Denmark.
Trial duration	Enrolment duration: 9 months
Number of patients	40 patients. WHO Group I PAH: 10 with IPAH, 10 with CTD-aPAH, WHO Group III: 10 with pulmonary disease related PH and Group IV: 10 with CTEPH.
Study treatment	Patients with PAH/PH will be consecutively selected from the cohort of patients being treated with PAH specific medication, and incident cases will be enrolled prospectively.

ASPIRE: ArrhythmiaS in Pulmonary arterial hYPERtension and right heart failure assessed by continuous long-term cardiac monitoring

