Selection criteria	
Inclusion criteria:
 
The following patients will be included in the study:
 
 - Patients >18 years of age - Patients on current PAH specific medication must be stable for at least 3 months. - Patients can be included in WHO group 1 only with IPAH or CTD-aPAH and group IV, CTEPH 
Exclusion Criteria:
 
 - Patients who are unlikely to comply with the study protocol and procedures required by the study protocol. - Patients with any severe complication or comorbidity other than PAH which might determine the prognosis and functional level of the patient. - Need for escalation of PAH specific therapy - Patients who are already in specific treatment for arrhythmias. 
Concomitant treatments
 
 - Patients can be on the following treatments only if they have been at least treated for three months prior to inclusion and are planned to be continued during the whole study period: diuretics, digoxin, beta-blockers and amiodarone
Data collection	
At screening:
 
 - PAH verified with right heart catheterization before start of PAH specific medication. - Basic demographic data including medication. - Physical examination and vital signs - 6 MWT - Digital ECG to verify rhythm at baseline 
Care Link Network
 
 - Device information send from home - Clinicians review device data on the Medtronic CareLink Clinician Website 
Visits every 6 months
 
 - 6 MWT - Lab tests, including NT-proBNP - Record concomitant medications
Statistical methods	
SPSS/PASW Statistics 19 software (SPSS Inc, Chicago IL), SAS or R are used for all statistical analyses.
 
In addition, descriptive time serial analysis will be done on heart rate variability and heart rate.
 
Correlation statistics will be done to assess heart rate variability and heart rate in correlation to known risk markers in PH.

Endpoints	To assess the incidence of arrhythmias in patients with PAH.

Study Chart - ASPIRE I

	Screening	Operation	Visit 1	Visit 2	Visit 3	Visit 4
Informed consent	X	1	6 mo	12 mo	18 mo	24 mo
Height	X					
Weight	X					
RHC ^a	X					
SPECT/CT	X					

ASPIRE: ArrhythmiaS in Pulmonary arterial hYPERtension and right heart failure assessed by continuous long-term cardiac monitoring

LFT	X					
ECG	X	x	X	X	x	X
Echocardiography	X			x		x

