Study design	Single centre observational study with CMR and insertable cardiac long term monitoring in newly referred and PAH patients treated with PAH-specific therapy. Patients will be followed for 2 years after inclusion.
Study objectives	Primary objective To evaluate CMR as a tool for providing noninvasive predictors for arrhythmias in patients with PAH. Secondary objectives

ASPIRE: ArrhythmiaS in Pulmonary arterial hYPERtension and right heart failure assessed by continuous long-term cardiac monitoring

	
 - To assess change in 6 MWT - To assess hemodynamic changes with RHC - To assess hemodynamic changes in echocardiography - To assess the number of patients progressing one FC (Modified NYHA class) - To assess changes in NT-proBNP. - To assess Hospital admission for any reason - To assess Death or transplantation
Methodology	The study will be conducted as a single center study at Copenhagen University Hospital, Rigshospitalet, DK-Denmark.
Trial duration	Enrollment duration: 9 months
Number of patients	40 patients. WHO Group I PAH: 10 with IPAH, 10 with CTD-aPAH, WHO Group III : 10 with pulmonary disease related PH and Group IV: 10 with CTEPH.
Selection criteria	
Inclusion criteria:
 
The following patients will be included in the study:
 
 - Patients >18 years of age - Voluntary participation after giving informed verbal and written consent - Patients untreated with PAH specific therapy - Patients on current PAH specific medication independent of duration of therapy - Patients can be in WHO group 1 only with IPAH or CTD-aPAH, and group IV, CTEPH 
Exclusion Criteria
 
 - Patients who are unlikely to comply with the study protocol and procedures required by the study protocol. - Patients with any severe complication or comorbidity other than PAH which might determine the prognosis and functional level of the patient. - Renal insufficiency (GFR estimated <60 ml/min/ 1.73 m²). - Implanted ferromagnetic metal parts unsuited for CMR (ICD, cerebral clips) - Claustrophobia - Allergy or hypersensitivity to Gadovist 
Concomitant treatments
 
 - Patients can be on the following treatments only if they have been at least treated for three months prior to inclusion and are planned to be continued during the whole study period: diuretics, digoxin, beta-blockers, amiodarone

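### ASPIRE I and II plan 10 WHO Group III patients among the 40, but no inclusion criterion in either synopsis admits Group III

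*Combined protocol and SAP*

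**What the plan says.** ASPIRE I, Number of patients, plans 40 in total: "WHO Group I PAH: 10 with IPAH, 10 with CTD-aPAH", followed by "WHO Group III: 10 with pulmonary disease related PH and Group IV: 10 with CTEPH". The Selection criteria row of that synopsis then states "Patients can be included in WHO group 1 only with IPAH or CTD-aPAH and group IV, CTEPH".

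ASPIRE II has the same pair of rows. Its quota includes "WHO Group III : 10 with pulmonary disease related PH and Group IV: 10 with CTEPH", and its inclusion line is "Patients can be in WHO group 1 only with IPAH or CTD-aPAH, and group IV, CTEPH".

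ASPIRE III repeats the quota of 40. Its inclusion line admits patients whatever their underlying disease, but adds WHO group 1 in brackets.

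The ASPIRE I primary objective is "To assess the incidence of arrhythmias in prevalent and incident cases of PAH using continuous long-term monitoring", and its endpoint is "To assess the incidence of arrhythmias in patients with PAH". Apart from naming software, its Statistical methods row covers only heart rate and heart rate variability, beginning "In addition, descriptive time serial analysis will be done on heart rate variability and heart rate" and going on to correlations with risk markers. It does not define the population for the incidence.

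**The concern.** Two rows of one synopsis describe different populations, and this happens in two of the three sub-studies. Each inclusion line starts with group 1, restricts it to two subtypes, and then goes on to name group IV. It therefore reads as the list of admitted groups, with Group III left out.

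The practical stake is at screening. A patient with PH due to lung disease is wanted by the quota row and not admitted by the inclusion line, so staff depart from one row or the other whichever they follow. Participation involves an implanted monitor, so eligibility should not depend on which row is consulted.

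The second stake is reporting. The ASPIRE I result is described as an incidence in PAH, whereas the quota row attaches the PAH label to its Group I patients and plans to enrol Groups III and IV as well.

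**Working it through.** **Inputs**, from the Number of patients and Selection criteria rows of the three synopses: four planned groups of 10 (IPAH, CTD-aPAH, Group III, CTEPH), and the groups that each inclusion line names.

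**The plan's own total.** 10 + 10 + 10 + 10 = 40. This reproduces the stated number. The documents give no alpha, power, effect size or dropout rate behind the 40, so there is no sample-size formula to check.

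**Quota against criteria, ASPIRE I and ASPIRE II.**

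| Group | Planned | Named in the inclusion line |
|---|---|---|
| IPAH | 10 | yes |
| CTD-aPAH | 10 | yes |
| Group III | 10 | no |
| CTEPH | 10 | yes |

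- Planned places covered by the criteria: 10 + 10 + 10 = 30.
- Planned places not covered: 40 − 30 = 10, and 10/40 = 25%.
- If N = 40 is kept and filled from the three listed groups: 40/3 ≈ 13.3 each, for example 14/13/13. N can be reached, but the split cannot.

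**ASPIRE III.** If the bracketed group 1 is a restriction, the 10 Group III and 10 CTEPH places fall outside it: 20 of 40. If the words admitting any disease govern, none do: 0 of 40. The text does not decide between these readings.

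**Does other text settle ASPIRE I and II?**

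- *Towards the broader population:* the ASPIRE I Study treatment row describes the source cohort as PAH/PH, and the heart rate variability objective refers to risk markers in PH.
- *Towards the narrower one:* both synopses exclude severe comorbidity other than PAH that could determine prognosis, which a screener might apply to the lung disease that defines Group III. ASPIRE II also lists lung function testing at screening for the purpose of excluding COPD and ILD. That line sits under Data collection and may be no more than diagnostic work-up. The ASPIRE I Data collection row has no such line.
- *Neutral:* Conclusions and perspectives describes patients spread equally over the subgroups of PAH. That fits two, three or four equal groups, so it does not discriminate.

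No section says which row takes precedence.

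**Precision of a by-group report.** With 2 events in 10 patients (an illustrative count), the exact (Clopper-Pearson) 95% interval is 2.5% to 55.6%.

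**The case against.** The best defence is grammatical. The word only stands next to group 1 and may limit the subtypes within that group, not the list of groups. No exclusion criterion names Group III. On this reading the line is incomplete, not prohibitive. The quota including Group III appears three times, and the PAH/PH wording in ASPIRE I supports it, so the broader population may well be what was meant.

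Much of this stands as evidence of intent. It does not remove the mismatch. If the line concerned group 1 subtypes alone, it would have no reason to go on to CTEPH. Even on the lenient reading, no criterion in ASPIRE I or II admits Group III, and the omission occurs in two separately worded lines.

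It is also fair to say that this is a single-centre observational study in which no planned analysis compares or stratifies by diagnostic group. No stated test relies on 10/10/10/10. That objection stands and limits the consequence.

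Four stronger conclusions are tempting, and the documents do not support them:

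- *That the study is capped at 30.* The criteria limit which groups enter, not how many patients; only the split fails.
- *That ASPIRE III is a third contradiction.* Its line is ambiguous. Its wording that SPECT/CT is to exclude embolism, where ASPIRE II says to evaluate it, concerns embolism and not Group III.
- *That settling Group III alone fixes the ASPIRE I denominator at 20, 30 or 40.* It also depends on whether CTEPH counts as PAH, and the protocol uses the term loosely: the supraventricular arrhythmia background calls a cited cohort that included chronic thromboembolic disease a PAH cohort. A 14/13/13 enrolment would also give 26 or 27 Group I patients, not 20.
- *That the incidence is distorted by a calculable amount.* The documents give no arrhythmia rate for Group III, so any such figure would rest on an assumed rate.

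**Conclusion.** The point holds as an internal inconsistency in ASPIRE I and ASPIRE II. In each, 10 of 40 planned patients (25%) have no criterion that admits them, and the quota row and inclusion line cannot both be followed. This rests only on the wording of the two rows and on the absence of any text giving one of them precedence. It needs no assumption about event rates.

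The ASPIRE III criterion is unclear but is not shown to be wrong. The documents do not reveal which population is intended, although some of the wording favours the broader one. The consequence is for eligibility decisions, for the planned composition and for how the ASPIRE I incidence is labelled. No effect on power or on a planned test is shown.

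**What to change.** Reconcile the Number of patients row and the inclusion line in ASPIRE I and II so that the groups admitted are the groups counted, or restate the strata and N to match the criteria. Which eligibility rule is right is for the sponsor and investigators, and this review does not choose it. In the same amendment, rewrite the ASPIRE III inclusion line so that it has one reading, and make clear in ASPIRE II whether the lung function line is an eligibility rule or diagnostic work-up.

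In ASPIRE I, state which groups form the denominator of the incidence. If Groups III or IV are included, call the pooled figure an incidence in PH, and show incidence by diagnostic group with exact intervals.

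The cost is a wording amendment to three synopses and a line or two on the ASPIRE I analysis. No extra patients are needed. If the quota governs, the total stays at 40. If the criteria govern, the 10 Group III places are dropped (leaving 30) or reallocated (about 13 per listed group). The drawback of by-group reporting is very wide intervals, as the 2/10 example shows, so it should be descriptive only.

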Data collection	
At screening:
 
 - SPECT/CT will be performed at diagnosis for prevalent cases only and at screening for incident cases to evaluate pulmonary embolism - LFT to exclude pulmonary disease: COPD and ILD - Echocardiography to exclude left heart disease - PAH verified with right heart catheterization before start of PAH specific medication - Basic demographic data including medication. - Physical examination and vital signs - 6 MWT - ECG - Lab tests including liver and renal function tests and NT-pro-BNP 
Visits every 6 months or with increased symptomatology
 
 - CMR with measurement of RV/LV volumes, CI (volumetric and flow), RVEF and pulmonary artery diameter according to standard criteria. Yearly measurement of RV fibrosis (LGE, T1 mapping and ECV). The same MR-scanner must be used for all measurements.

ASPIRE: ArrhythmiaS in Pulmonary arterial hYPERtension and right heart failure assessed by continuous long-term cardiac monitoring

	
 - 6 MWT - Lab tests, including liver and renal function tests including yearly eGFR, hematocrit and NT-proBNP - Echocardiography yearly and at 3 month after inclusion - Record concomitant medications - PAH medications
Endpoints	
Coprimary endpoints
 
 - Change in cardiac index, right atrial size, RV size, fibrosis and stroke volume - Arrhythmias as assessed by Insertable Cardiac Monitors 
Secondary endpoints
 
 - Modified NYHA functional class - Reduction in 6 MWT in the study period. - NT-proBNP change in study period. - Change and /or escalation of PAH therapy - Respiratory hospitalization - Death or transplantation

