Statistical methods	
Repeated measurements of CI, right atrial size, RV size, fibrosis and stroke volume will be performed every 6 months.
 
Two groups of subjects will be defined: 1. Patients with no change in CI, RV size and stroke volume, and 2. A group of patients where one of the measurement change more than 2 standard deviations.
 
It is group-shift (Y/N) if a subject changes out of the 2 stdv band.
 
Time to group shift will be analysed in a subsequent analysis.
 
Cox-model analysis will be done on measurements of (1) cardiac index, (2) RV size, (3) stroke volume and (4) fibrosis to calculate the correlation with risk of developing clinical symptoms and clinical deterioration. In other words, this analysis will establish if the MR-measurements predict clinical outcome.
 
SPSS/PASW Statistics 19 software (SPSS Inc, Chicago IL), SAS or R is used for all statistical analysis.

MRI protocol

Every six months, all subjects are scanned according to the protocol below. The scanning will take 60-80 minutes. MRI scans will be carried out on a 1.5 to 3.0 Tesla MRI scanner. At visit 1, 3 and 5 a cannula will be placed for contrast administration.

MRI studies will provide time-volume curves for LV and RVs filling and ejection fraction, peak emptying rate, peak filling rate and stroke volume will be calculated.

The measurements will provide time-flow curves for flow in the pulmonary trunk, pulmonary branch arteries and aorta. It will be possible to measure the distribution of flow to the right and left lung. Since the pulmonary trunk is often dilated with slow flow, it can be more accurately to measure the flow in the smaller branch pulmonary arteries.

Angiography will also provide the flow distribution in the lungs and the different segments of the lungs.

After baseline scan subjects will be exercised by a MR compatible ergometer with a load of 1 watt per kg. Stress test will measure the physiological reserve in terms of changes in cardiac index and ventricular volumes. Finally, late enhancement will measure the degree of fibrosis in the left and right ventricle.

Scannings protocol		Sekvens
1	Scout	SSFP, single shot
2	Transverse stack, no gaps – covers the hearts	SSFP, 8 mm, 25 phases

ASPIRE: ArrhythmiaS in Pulmonary arterial hypertension and right heart failure assessed by continuous long-term cardiac monitoring

3	LV vertical long axis (VLA)	SSFP, 8 mm, 25 phases
4	Scout LV, short axis	SSFP, single shot

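### ASPIRE II makes change in five CMR measures a coprimary endpoint but analyses that change only as leaving a 2 SD band, which loses power that a continuous repeated-measures model would keep

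*Combined protocol and SAP*

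**What the plan says.** In the Study Synopsis for ASPIRE II, the Endpoints row lists two coprimary endpoints: "Change in cardiac index, right atrial size, RV size, fibrosis and stroke volume" and "Arrhythmias as assessed by Insertable Cardiac Monitors".

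The Statistical methods row then sets out how change is handled:

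- Grouping: "Two groups of subjects will be defined: 1. Patients with no change in CI, RV size and stroke volume", against "A group of patients where one of the measurement change more than 2 standard deviations".
- Scoring: "It is group-shift (Y/N) if a subject changes out of the 2 stdv band".
- Follow-on: "Time to group shift will be analysed in a subsequent analysis". No method is named for this.
- A separate analysis: "Cox-model analysis will be done on measurements of (1) cardiac index, (2) RV size, (3) stroke volume and (4) fibrosis". Its outcome is clinical symptoms and clinical deterioration.

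On scan frequency, the MRI protocol says "Every six months, all subjects are scanned according to the protocol below", and the Study Chart shows CMR at implantation and at 6, 12, 18 and 24 months. The Data collection row makes fibrosis a yearly measurement, and the note under the scanning table limits contrast to three visits.

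The sample is 40 patients in four groups of 10. No sample-size calculation, alpha, effect size, SD or within-patient correlation is given.

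**The concern.** The coprimary endpoint is a change in continuous quantities measured repeatedly, but the only stated analysis of it as an outcome is a threshold crossing. A patient who worsens by 1.9 SD does not count as shifted, and one who worsens by 2.1 SD counts the same as one who worsens by 4 SD. The plan gives no estimate of how much any measure changes or how precisely that is known.

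With 40 patients there is little precision to spare. A real change in CMR measures, or a real difference in course between two sets of patients, could easily go unseen under this rule. Two of the five coprimary measures (right atrial size and fibrosis) are not named in the no-change group, so whether their change is analysed at all is unclear.

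**Working it through.** **1. Inputs from the plan.** 4 × 10 = 40 patients. Five scans each gives 40 × 5 = 200 planned scans, of which 40 × 3 = 120 can carry contrast. The plan states no power figure, so there is none to reproduce.

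**2. Where each coprimary measure is named.**

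| Measure | No-change group | Cox models | Scans per patient |
|---|---|---|---|
| Cardiac index | yes | yes | 5 |
| RV size | yes | yes | 5 |
| Stroke volume | yes | yes | 5 |
| Fibrosis | no | yes | 3 |
| Right atrial size | no | no | up to 5 |

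No row of the synopsis gives a continuous analysis of change as an outcome.

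**3. Illustration A (all values assumed).** One measure with total SD 1 and within-patient correlation 0.5. Scans are at 0, 0.5, 1, 1.5 and 2 years. There are 12 patients who diverge linearly by 1 SD over 24 months and 28 who do not. Two-sided alpha is 0.05, with no dropout.

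Continuous analysis (per-patient slope, two-sample t test):

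- Sum of squared time deviations: 1 + 0.25 + 0 + 0.25 + 1 = 2.5.
- SD of a slope: √(0.5/2.5) = 0.447.
- Standard error of the difference: 0.447 × √(1/12 + 1/28) = 0.447 × 0.345 = 0.154.
- True slope difference: 1 SD over 2 years = 0.5 per year, and 0.5/0.154 = 3.24.
- Normal approximation to power: Φ(3.24 − 1.96) = Φ(1.28) = 0.90. Simulation with the t test gives about 89%.

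Threshold rule on the same data (any follow-up scan more than 2 baseline SDs from the first scan, Fisher's exact test), by simulation:

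- Worsening only: about 26%.
- Two-sided band: about 13%.

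**4. Dependence on which SD is meant.** With the same set-up at correlation 0.8, the slope comparison is near 100%. The worsening-only rule runs from about 6% if the SD is the baseline SD to about 82% if it is the measurement-error SD.

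**5. Illustration B (different assumed values).** 20 v 20 patients, correlation 0.7 to 0.9, random-slope SD 0.25 SD per year, and the slope difference set so that the continuous analysis has about 80% power. The SD was read four ways: baseline, 24-month change, difference of two measurements, and measurement error.

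| Analysis | Two-sided band | Worsening only |
|---|---|---|
| Slope from five scans | 76–81% | 76–81% |
| Ever shifted, Fisher | 0–10% | 0–36% |
| Ever shifted, Pearson | 0–17% | 0–47% |
| Time to shift, log-rank | 0–15% | 0–45% |

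Time to shift does not restore the loss.

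**6. Chance crossings.** If the SD is that of the change itself, a stable patient leaves a two-sided band at one scan on one measure with probability 4.6% (40 × 0.0455 = 1.8 patients). For any of three independent measures this is 1 − (1 − 0.0455)³ = 13%. Over three measures and four follow-up scans it is up to 1 − (1 − 0.0455)¹² = 43%, treating all twelve as independent. Counting a shift on any one measure therefore also adds noise to the yes/no score.

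**The case against.** The strongest case against has five parts.

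- **The Cox models use the measurements with no 2 SD cut attached.** This stands. A reader might infer that the CMR data are thrown away, and the documents do not support that. The loss concerns change as an outcome. The Cox models answer another question, since their outcome is clinical deterioration, and they leave out right atrial size.
- **The size of the loss hangs on an undefined SD.** This also stands. If the SD is scan repeatability, a 2 SD cut is a defensible rule for real change in an individual, and the worsening-only rule kept about 82% power in one setting. A reader might instead use the textbook efficiency of a one-sided cut at 2 SD, φ(2)²/[p(1 − p)] = 0.0540²/(0.0228 × 0.9772) = 0.13, and conclude that 40 patients act like about 5 (0.13 × 40 = 5.2). That figure is a small-effect result for one measure, one cut and one reading of the SD, and the plan does not fix that reading.
- **The illustrations do not test the plan's exact rule.** They use one measure, whereas the plan counts a shift on any one of several. They also compare two sets of patients, a test the plan never attaches to the group shift. This is fair, so the percentages show direction and possible scale and are not the trial's power.
- **Baseline is used.** A reader might infer that the first scan is ignored. Change implies a reference value, most naturally that scan. What is absent is a model that uses it together with every later value.
- **Five scans do not apply to everything.** Correct: fibrosis has three.

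None of this supplies a continuous analysis of change.

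**Conclusion.** The point holds in a limited form. For a coprimary endpoint defined as change in continuous measures, the plan states only a threshold crossing and the time to it. Under every reading of the SD and direction tried, this lost power against a continuous analysis of the same scans. In illustration A the fall is from about 89% to about 26% (worsening only) or about 13% (two-sided). In illustration B it is from 76–81% to between 0 and 47%. All of these rest on assumed SDs, correlations and effect sizes. The direction is firm, but the size is not.

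Defining the SD and direction would be useful but would not remove the loss, because changes short of the cut would still not count. For right atrial size and fibrosis the gap may be that no analysis of change is stated at all. This should be changed because the remedy is cheap. It does not make the planned data unusable.

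**What to change.** In the Statistical methods row of the ASPIRE II synopsis:

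- Make the primary analysis of each of the five CMR measures a linear mixed model on all available continuous values. Keep the first scan as an outcome and do not also enter it as a covariate. Use fixed effects for time and diagnosis group, and a random patient intercept, with a random slope where it can be estimated (with three scans for fibrosis it may not be).
- Report mean change per year with a 95% CI for each measure, naming right atrial size and fibrosis explicitly.
- Keep the 2 SD group shift and time to shift as descriptive secondary summaries. State which SD is used, the direction, and which measures count.
- Do not use an arrhythmia-by-time interaction in this model as the test of the primary objective. That objective is for CMR to predict arrhythmias. The interaction would classify patients by events during the same follow-up and reverse the question.

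The cost is protocol wording and modest analysis work. No additional scans, patients or data are needed.

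### ASPIRE II group shift counts improvement and deterioration as the same event, and the SD that sets its band is not named

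*Combined protocol and SAP*

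**What the plan says.** All references are to the combined protocol and SAP.

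- Study Synopsis – ASPIRE II, Statistical methods, sets up two groups. The first has no change in cardiac index (CI), RV size and stroke volume. The second is "A group of patients where one of the measurement change more than 2 standard deviations". The event follows: "It is group-shift (Y/N) if a subject changes out of the 2 stdv band". Then: "Time to group shift will be analysed in a subsequent analysis".
- The next sentence of that section describes a separate Cox analysis of the MR measurements, intended "to calculate the correlation with risk of developing clinical symptoms and clinical deterioration".
- The same section opens with a longer list: "Repeated measurements of CI, right atrial size, RV size, fibrosis and stroke volume will be performed every 6 months". Under Data collection, however, fibrosis appears as "Yearly measurement of RV fibrosis (LGE, T1 mapping and ECV").
- Under Endpoints, the first coprimary endpoint is "Change in cardiac index, right atrial size, RV size, fibrosis and stroke volume", also without direction.
- Inclusion criteria admit patients not yet on PAH therapy and patients on it for any duration. A change or escalation of PAH therapy is a secondary endpoint. The section on recruitment says new patients will be offered participation.
- The Study Chart – ASPIRE II places a CMR at implantation and at 6, 12, 18 and 24 months. Data collection lists CMR under "Visits every 6 months or with increased symptomatology".

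**The concern.** The rule speaks of change without a sign, and a band has two limits. A rise in CI after starting therapy and a fall in CI from RV failure both become a Yes, with the same kind of event time. The protocol's own background shows why direction matters. Table 1 of Project ASPIRE II (univariate echocardiographic predictors of supraventricular arrhythmia in IPAH) gives a hazard ratio of 2.76 for RV diameter and 0.72 for cardiac output, so a larger RV goes with more risk and a higher output with less. A Yes/No variable that pools both directions mixes patients whose expected risks differ in sign.

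The second issue is the width of the band. The text fits the SD of change in stable patients, the SD of change in this cohort, the SD of a single scan, or the SD between patients. If the choice is made once the data are visible, the number of events is chosen with it.

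At stake is the only rule in that section that turns the coprimary CMR change endpoint into a patient-level outcome.

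**Working it through.** The plan gives no SD, reliability, expected number of shifts or power for this analysis, so there is no figure to reproduce.

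**Inputs from the documents.** Limit 2 SD; any one measure suffices; CI, RV size and stroke volume (the likeliest reading); one implantation scan and 4 follow-up scans, so 3 × 4 = 12 comparisons; 40 patients.

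**Assumptions.** Implantation scan as reference, normal errors, correlations between measures from 0 to 0.9. Simulation of 300,000 patients per setting, with every change sharing the patient's one baseline scan.

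**Step 1: one comparison.** If the SD is that of change in stable patients, P(outside the band) = 2(1 − Φ(2)) = 4.55%. For three independent measures at one visit: 1 − (1 − 0.0455)³ = 13.0%. Twelve independent comparisons would give 1 − (1 − 0.0455)¹² = 42.8%. The shared baseline and the correlations lower this to 23–37% by simulation, which is 40 × 0.23 ≈ 9 to 40 × 0.37 ≈ 15 patients if all 40 were stable.

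**Step 2: other SDs.** Each limit is expressed in SDs of change. A single-scan SD gives 2/√2 = 1.41. A between-patient SD with reliability r gives 2/√(2(1 − r)), so 2.58 at r = 0.7 and 4.47 at r = 0.9.

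| SD used for the band | Limit, in SDs of change | Stable patients shifted by 24 months |
|---|---|---|
| Single scan | 1.41 | 59–81% |
| Change in stable patients | 2.00 | 23–37% |
| Between patients, r = 0.7 | 2.58 | 6–10% |
| Between patients, r = 0.9 | 4.47 | about 0.01% |

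If all five listed measures count, with fibrosis at 12 and 24 months only, there are 4 × 4 + 2 = 18 comparisons. The second row then becomes 26–51%.

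**Step 3: a wide band misses real change.** At r = 0.9, take a true fall of 2 SDs of change in both CI and stroke volume from 12 months. Each look flags 1 − Φ(4.47 − 2) = 0.67%. Over six looks the upper bound is 6 × 0.67% ≈ 4.0%, and simulation gives about 3–4%. A fall in one measure only is flagged in about 2%.

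**Step 4: direction (SD of change in stable patients).**
- A patient who truly improves by 1 SD of change in CI and stroke volume at every follow-up scan is labelled shifted in 52–67%, against 7–8% if only adverse moves count.
- Among stable patients labelled shifted, 26–50% moved only in the favourable direction.
- Counting adverse moves only lowers the stable-patient rate from 23–37% to 12–20%.

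**Step 5: price of the one-sided rule.** For a true deterioration of 2 SDs of change in one measure from 12 months, the share flagged falls from 82–83% to about 75–80% (82% at the most extreme correlation pattern). Part of the two-sided share is noise in the wrong direction.

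**The case against.** The strongest reply is that the rule does what its name says. It separates no change from change, and the endpoint it serves is change without a sign. Deterioration is named only in the separate Cox sentence. A reader might infer that time to group shift is meant as a measure of prognosis and fails at it. The documents do not support that, because no passage says what time to group shift is for. What stands is narrower: as written, the event cannot be interpreted by direction.

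A reader might also infer that about a third of stable patients will be falsely labelled. That is not supported either. The rate runs from near 0% to 81% with the choice of SD, and the upper ends need independent errors, although CI and stroke volume come from the same scan.

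It can also be said that direction is the smaller part. In an assumed cohort of 5 responders, 30 stable and 5 deteriorating patients, with the SD of change, stable patients supply 50–58% of shifts under the two-sided rule and still 44–54% under an adverse-only rule. This is fair, and it is why the SD must be named as well. The cohort split is itself assumed, since the documents do not say how many patients will be untreated.

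Finally, the three-measure reading is not certain. The unnamed SD, the status of right atrial size and fibrosis, and the handling of symptom-triggered scans are mainly missing detail.

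**Conclusion.** The point holds in this form. As written, group shift gives a patient who improves and one who deteriorates the same event, in a study that admits untreated patients and expects some therapy changes. Time to group shift then has no directional meaning. This follows from the text and needs no assumed number.

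The contribution of scan noise is conditional. It rests on assumed normal errors, assumed correlations and an SD the plan leaves open. The range itself is the finding: depending on the SD, the same rule flags almost no stable patients, and few deteriorating ones, or flags most stable patients.

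A reader might go further and conclude that ASPIRE II's prediction analysis is compromised. It is not: the Cox analysis uses the measurements and not the group-shift label, and nothing links group shift to the primary objective of predicting arrhythmias. The problem is confined to the group-shift and time-to-shift analyses. It should be corrected because a better definition is available at little cost.

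**What to change.** Change the ASPIRE II statistical methods as follows.

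1. Define adverse shift as CI down, stroke volume down or RV size up by more than 2 SD from the implantation CMR. Define favourable shift as the opposite moves, in a separate category.
2. Analyse time to adverse shift. Report favourable shift and any-direction shift alongside, so nothing in the present rule is lost.
3. Fix one SD per measure, with its source, before the analysis. The SD of change in stable patients over a comparable interval fits the purpose but needs a source outside these documents. If only short-interval scan–rescan data exist, say so, because the band is then narrower. At 0.8 of the stable-change SD, false shifts would be 23–40% adverse-only and 46–67% two-sided.
4. Say whether right atrial size and fibrosis count, with their adverse direction, and reconcile the six-monthly and yearly statements for fibrosis. Place changes between zero and 2 SD in a group, since as worded they fit neither.
5. State how death or transplantation before a scan is handled.

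Optional: a sensitivity analysis requiring the shift at two consecutive scheduled scans, and a rule for symptom-triggered scans.

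The cost is SAP wording, with no extra scans or patients. The downsides are fewer events and the small loss of detection shown in step 5. The optional confirmation would cost much more detection (42–43% flagged in the same case), so it should not replace the main analysis.
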